8.2 Detection of Bias

Patients will be assigned to treatment by a randomization schedule developed and maintained by an independent party. The treatment in this study will be blinded to the subjects, investigators, any individual conducting the study (e.g., nursing and pharmacy staff) and clinical study personnel. Participants will be assigned to treatment by a randomization schedule developed and maintained by an independent statistician.

Study drug and placebo will be provided as blinded investigational product (IP) with appropriate labeling to link to the randomization code. Where required, safety personnel and/or investigator may be unblinded to a particular subject's treatment assignment to meet reporting requirements to Regulators. Any breaking of the blind for individual subjects by the blinded clinicians will be documented in the clinical study report. Data collected after unblinding will be noted.

8.3 Outliers

No formal outlier tests are planned. Values that are outside the pre-defined range would be queried and excluded, if necessary, prior to database lock.

8.4 Testing/Validation Plan

All statistical analyses will be programmed using SAS® software version 9.4, or later. Graphic displays may be produced using R, version 3.0.0, or later. Standard macros will be used in programming when possible. Testing and validation plans for all programs will be developed in accordance with contract research organization guidelines and will include independent programming of tables and analyses.

9. STATISTICAL METHODS OF ANALYSIS

9.1 General Principles

Data will be summarized by each treatment arm and by pooled Control and Ampion arms. Descriptive statistics on continuous variables will include mean, standard deviation, median, 25th, and 75th percentiles, range, and 95% confidence intervals. Change from baseline will include a 95% confidence interval. Categorical variables will be summarized using frequency counts and percentages. Data listings of individual subject's data will be provided.

9.2 Subject Accountability

The number of subjects who are randomized, receive study drug, and complete the study will be summarized. The number of subjects included in the safety and ITT analysis sets will be included in the table. Attendance at each assessment (see Schedule of Assessments), including missed visits, discontinuations, lost to follow-up, and percentage accountability will be summarized. A list of subjects who withdraw early will be provided. It will include the reason and timing of the withdrawal. Similarly, the reason any subject is excluded from an analysis set will also be provided. In addition, significant known protocol deviations will be noted for individual subjects; a summary table may also be provided.

9.3 Demographic and Baseline Characteristics

Demographic (e.g., age, sex, race, ethnicity) and baseline characteristics (e.g., weight, height, comorbidities) will be summarized using descriptive statistics overall and by treatment group for the ITT and safety analysis population.

9.4 Medical History and Physical Examination

The number and percent of participants with past and current medical disorders at the time of randomization will be presented overall and by treatment group for the ITT and safety analysis population.

9.5 Safety Analyses

Safety data will be presented by treatment arm. Safety data will be evaluated by changes in vital sign measurements, laboratory assessments, and the frequency and severity of AEs. Concomitant medication will be recorded for safety. AEs will be collected from baseline to Day 60. The severity of AEs (mild, moderate, severe), relatedness (related, possibly related, unrelated) along with the duration, action taken, and outcome (e.g., study withdrawal) will also be recorded.

All data collected under this study protocol will be included in the assessment of patient safety. Missing or incomplete AE data will assume greatest relationship to study drug and/or severity.

Remaining safety data will be collected from enrollment through index hospitalization until hospital discharge (or in-hospital death). Safety data will be tabulated and presented overall and by treatment group for the safety analysis population.

9.5.1 Adverse events

Adverse events will be grouped by system organ class and by preferred term within system organ class according to the latest version of the MedDRA coding dictionary. The number of subjects reporting at least 1 adverse event and each adverse event will be summarized treatment group. Tables and/or narratives of any on-study death, serious or significant adverse events, including early withdrawals because of adverse events, will be provided should they occur.

9.5.2 Concomitant Medications

The number and percent of patients receiving concomitant medications or treatments prior to and during the study and at the final visit will be tabulated and presented overall and by treatment group for the ITT analysis dataset. Concomitant medications and treatments will be summarized using descriptive statistics and will be presented by type of drug (WHO DRUG classification preferred term and Anatomical Therapeutic Chemical Classification [ATC] level 1) overall and by treatment group for the safety and ITT analysis populations. There should be no significant differences in the use of concomitant treatments between groups. All concomitant therapies will be recorded to be able to compare any inadvertent imbalances between the groups.

9.5.3 Clinical Laboratory Tests

Hematology and chemistry data will be listed for each subject. Values outside the normal laboratory reference range will be flagged as high or low on the listings. Depending on the size and scope of changes in laboratory data, summaries over time and/or changes from baseline over time may be provided. Similarly, depending on the size and scope of the changes, shift tables showing baseline to post-baseline categorization that are below, within, and above normal range may be provided.

9.5.4 Vital Signs

Vital signs will be listed for each subject. These will include temperature, respiration, pulse, and blood pressure. Summaries over time and changes from baseline will be provided.

9.6 Efficacy Analyses

The efficacy of treatment on the clinical course and outcome of COVID-19 will be evaluated by comparing to placebo. Summaries will be performed by severity (severe or critical), individually, and combined.

Unless otherwise specified, continuous variables will be summarized with the number of non-missing observations, mean, standard deviation, median, minimum, maximum and 95% confidence intervals displayed. Data transformation or use of rank-based tests may be used if endpoints depart substantially from a normal distribution. Categorical data will be summarized as counts, percentages and 95% confidence intervals.

Differences between treatments will be presented using mean differences and 95% confidence intervals. Endpoints will be compared between treatment groups (Ampion or control).

Except where otherwise specified, missing data will not be estimated or carried forward in any of the descriptive analyses. No multiple comparison adjustment will be done for the secondary efficacy analyses. If the data clearly violate the distribution assumptions of the model, then transformations may be applied, or rank-based methods used.

The efficacy analyses of the endpoints are detailed in Section 3 and Section 4 above.

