4. HYPOTHESES

The primary endpoint assesses the effect of Ampion compared to placebo on clinical improvement. Clinical improvement is measured as the change in ordinal scale from baseline through Day 5 and Day 28.

Let μ_A and μ_S represent the mean changes in the ordinal scale for the three time points for Ampion and control respectively. Then it is desired to demonstrate that the mean change for Ampion is different than the corresponding mean change for the control, respectively. Formally, this is presented as:

$$H_0: \mu_A = \mu_S \text{ versus } H_A: \mu_A \neq \mu_S$$

The difference between Ampion and Placebo with respect to the change from baseline through Day 5 and Day 28 will be tested utilizing a Wilcoxon rank-sum test via PROC NPAR1WAY. To assess any potential time trends, an exploratory repeated measures analysis of variance will be performed with terms for treatment, time, and the interaction between the two. This will be done utilizing PROC GLM with the REPEATED option.

Secondary endpoints assess the effect of inhaled Ampion treatment compared to placebo on the clinical outcomes for participants with respiratory distress due to COVID-19. The secondary endpoints will be tested in a hierarchical manner in the order presented, and thus no adjustment to the alpha level is necessary:

Objective	Endpoint
Secondary	
Assess the effect of Ampion compared to placebo on safety	
Incidence of adverse events (AEs) and serious adverse events (SAEs) from baseline to Day 60.
Assess the effect of Ampion compared to placebo on clinical health	
Change in NEWS2 score from baseline through Day 5.Change in NEWS2 score from baseline to hospital discharge.
Assess the effect of Ampion compared to placebo on hospital stay	
Hospital length of stay (LOS) from admission to discharge.
Assess the effect of Ampion compared to placebo on oxygen use	Change in baseline in oxygen use, blood oxygen saturation, and oxygen flow rate from baseline through Day 5.
Assess the effect of Ampion compared to placebo on progression to respiratory failure	Percentage of participants who progress to respiratory failure (i.e., need for mechanical ventilation, ECMO, non-invasive ventilation) by Day 28.

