4.6 Intensive Care

Intensive care is measured by the proportion of participants who require Intensive Care Unit (ICU) admission by Day 28, ICU-free days through Day 28, and ICU LOS from ICU admission to discharge.

There are two endpoints in this set. Hypotheses about both will be tested independently. The first hypothesis about the percentage of patients who are admitted to the ICU involves all patients. The second hypothesis involves only patients who are admitted to the ICU. Since it is not known how many patients will be admitted to the ICU, the testing of the second hypothesis will be considered exploratory and not part of the hierarchical testing scheme

The first hypothesis to be tested is:

$$H_0: \pi_A = \pi_S \text{ versus } H_A: \pi_A \neq \pi_S$$

Where π_A and π_S represent the percentage of patients who are admitted to the ICU for Ampion and Placebo during the first 28 days after randomization. The difference between Ampion and Placebo will be tested via an appropriate chi-square test or Fisher's exact test utilizing PROC FREQ with the EXACT option, if needed.

The second hypothesis to be tested is:

$$H_0: \text{Median}_A = \text{Median}_S \text{ versus } H_A: \text{Median}_A \neq \text{Median}_S$$

Where Median_A and Median_S are the median ICU length of stay for the Ampion and placebo groups through Day 28 and discharge. Assuming there is no censoring, this will be tested using the Wilcoxon rank sum test via PROC NPAR1WAY. If censoring occurs, e.g., death, then the log rank test will be used based on PROC LIFETEST.

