7. INTERIM ANALYSIS AND EARLY STOPPING GUIDELINES

7.1 Interim Analysis

The interim analysis is planned near the end of enrollment, after 150 patients, to test the protocol assumptions and estimates for clinical improvement, all-cause mortality rates and secondary endpoints as the available information and nature of the COVID-19 pandemic is rapidly evolving, which may impact estimates for both Ampion and control. The interim analysis will be used to determine if the sample size should remain at the planned 200 patients or increase based on the results of this analysis.

The interim analysis will be conducted on the primary and secondary endpoint data at an alpha level of 0.001, and thus the overall alpha level for the final test will be performed at $\alpha=0.047$ instead of the nominal value of $\alpha=0.05$. The sponsor also reserves the right to alter the final sample size if the assumptions of clinical improvement are not satisfied at this interim analysis.

The interim analysis uses the same hypothesis test described in the final analysis where μ_A and μ_S represent the mean changes in the ordinal scale for Ampion and control respectively. Then, it is desired to demonstrate that the mean change for Ampion is different than the corresponding mean change for the control, respectively. Formally, this is presented as:

$H_0: \mu_A = \mu_S$ versus $H_A: \mu_A \neq \mu_S$

The difference between Ampion and Placebo with respect to the change from baseline at Day 5 and Day 28 will be tested utilizing a Wilcoxon rank-sum test. To assess any potential time trends, an exploratory repeated measures analysis of variance will be performed with terms for treatment, time, and the interaction between the two.

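### The ordered secondary tests are not made conditional on the primary endpoint, so error is not controlled across the primary and secondary families together

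*SAP*

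**What the plan says.** SAP Section 4 states: "The secondary endpoints will be tested in a hierarchical manner in the order presented, and thus no adjustment to the alpha level is necessary". Protocol 9.4.2 carries the same sentence. The list that follows holds secondary endpoints only: AE/SAE incidence first, then NEWS2, hospital stay, oxygen use, respiratory failure and intensive care, with Day 28 mortality last. Neither place mentions the primary result as a condition, and neither writes out a rule to stop at the first failure; the word hierarchical only implies one.

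The primary endpoint is defined separately: "Clinical improvement is measured as the change in ordinal scale from baseline through Day 5 and Day 28". No rule says whether both time points, either one, or a fixed order decides success.

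SAP 7.1 tests primary and secondary data at the interim at 0.001 and says "thus the overall alpha level for the final test will be performed at" 0.047.

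SAP 9.6 says "No multiple comparison adjustment will be done for the secondary efficacy analyses", and closes with "The efficacy analyses of the endpoints are detailed in Section 3 and Section 4 above". SAP 4.6 takes the second ICU hypothesis out of the ordering as "considered exploratory and not part of the hierarchical testing scheme", so it treats the ordering as in force.

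**The concern.** A fixed sequence of single tests, stopped at the first failure, protects its own family at full alpha. It protects the study as a whole only if it starts after the primary has succeeded. Here the sequence starts at its own first member, whatever happened to the primary. A trial that missed its primary could still declare secondary results significant and cite the statement that no adjustment was needed.

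The sample-size text makes this more than a formality. It is still built on mortality, now the last secondary endpoint, and no power is given for the ordinal primary. If the primary fails, interest will turn to the secondaries, and the plan does not say that they are then descriptive.

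**Working it through.** **Inputs**
- Final level 0.047 and interim level 0.001: SAP 7.1 and Protocol 9.2.3.
- Interim after 150 of 200 patients, so information 150/200 = 0.75.
- Two-sided testing: SAP Section 4 ("it is desired to demonstrate that the mean change for Ampion is different than the corresponding mean change for the control").
- Order of the secondary list: SAP Section 4 and Protocol 9.4.2.
- Correlation between test statistics: not given. I assume 0 to 0.8 and treat each step as a single test.

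**1. The plan's own alpha split.** 0.001 + 0.047 = 0.048 is an upper bound. Allowing for the correlation √0.75 = 0.866 between interim and final statistics, the joint error is 0.0470. The split holds 5% for one endpoint at fixed sample size. It does not address two families.

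**2. No gate, one primary test and one opening secondary step, both null.** Independent: 1 − (1 − 0.047)² = 1 − 0.953² = 1 − 0.9082 = 0.0918. Correlated values are simulated from normal test statistics (1,000,000 draws).

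| Correlation | No gate | Gated on the primary |
|---|---|---|
| 0 | 9.2% | 4.7% |
| 0.5 | 8.5% | 4.7% |
| 0.8 | 7.3% | 4.7% |

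Direct integration of the bivariate normal gives 8.6% and 7.4% for the last two rows; the difference is simulation error and rounding. With a gate and everything null, a false secondary claim needs a false primary first, so the total stays at 0.047.

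**3. The list as written, AE/SAE incidence first.** A secondary-efficacy claim then needs the AE step and NEWS2 both significant. All null and independent, a false primary or secondary-efficacy claim has probability 0.047 + 0.953 × 0.047² = 0.047 + 0.0021 = 0.0491. Simulated (8,000,000 draws): about 5.3% at correlation 0.5 and 5.4% at 0.8. A secondary-efficacy claim after a failed primary occurs in 0.2%, 0.6% and 0.7% of trials respectively.

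**4. When the AE step does not block.** Let w be the chance that the AE step is significant. With independence, the error for primary or secondary efficacy is 0.047 + 0.953 × 0.047 × w = 0.047 + 0.0448w.
- w = 0.047 (AE null): 0.0491.
- w = 0.5: 0.0694.
- w = 1: 0.0918.

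SAP 4.1 tests AE incidence two-sided, so a true difference in either direction raises w. SAP 4.8 says AE and SAE rates are tabulated without statistical testing. If that governs, the AE step disappears, NEWS2 opens the chain, and step 2 applies in full.

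**5. The two-time-point primary.** If success at either Day 5 or Day 28 counts, the ungated error is 1 − 0.953³ = 13.4% if independent and 9.2% at correlation 0.8. Adding the gate alone leaves 9.2% and 7.3%. The gate delivers 0.047 only with a rule that both must succeed or that one is tested before the other.

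**The case against.** Four points can be made for the plan.

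- **The sentence concerns the secondary endpoints only.** Within that family, full alpha at each ordered step is correct for single tests with a stop at first failure. This stands: a reader might infer that the no-adjustment statement is simply false, and it is not. It fails across primary plus secondaries. It is also unsupported inside steps that hold several endpoints (two for NEWS2, three oxygen measures; in the ICU set, "There are two endpoints in this set. Hypotheses about both will be tested independently", although one of those is then taken out of the ordering). Nor does SAP 7.1 claim control across both families; its 0.047 concerns interim and final looks.

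- **SAP 9.6 restates the ordering.** A reader might infer that SAP 9.6 abandons multiplicity control. The documents do not support that. A fixed sequence involves no adjustment of individual tests, SAP 9.6 defers to Section 4, and SAP 4.6 keeps the scheme. Error rates for a set of unordered secondary tests therefore do not describe this plan. What remains is ambiguity for someone who reads SAP 9.6 alone.

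- **The AE step blocks the chain.** This also stands under the global null: 9.2% is not the risk of a false efficacy claim in the listed order, and 4.9% to 5.4% is. But that protection is accidental. It weakens if event rates differ and vanishes if SAP 4.8 governs.

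- **This is a Phase II trial meant to guide development.** The documents describe no confirmatory claim resting on secondary endpoints. That limits the stakes, but the plan invokes formal hierarchical testing, so its terms should be complete.

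**Conclusion.** The concern holds in a limited form. No gate on the primary is written in either document, so the primary and the secondary chain each run at 0.047 and are not jointly controlled. Counting any false claim, including an AE difference, the error is 9.2% if independent and about 7.3% at correlation 0.8, against 4.7% with a gate. Counting only primary or secondary-efficacy claims in the listed order, it is 4.9% to 5.4% with everything null, and about 7% to 9% if the AE step is removed or passes almost surely. These figures rest on assumed correlations, one primary test and one test per step; the undefined Day 5/Day 28 rule would make them larger if either time point counts as success. The defect is an incomplete testing rule that is cheap to close.

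**What to change.** In SAP Section 4 and Protocol 9.4.2, add wording such as: *Formal testing of the secondary sequence begins only if the primary endpoint has been met at the level for that analysis, under the stated Day 5/Day 28 decision rule. Testing ends at the first step that is not significant; p-values after that point are descriptive.*

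Two things must accompany it. First, write the Day 5/Day 28 rule (both required, or one tested before the other), because a gate on an either-time-point primary does not hold 0.047. Second, reconcile SAP 4.1 with SAP 4.8 on whether AE/SAE incidence is a tested step, and name one ordered test per step. If the AE step is removed, the gate should be in place at the same time.

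Replace the SAP 9.6 sentence on multiple comparisons with a cross-reference to this rule.

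The change is to wording in the SAP and protocol; no data collection or sample size is affected. The price is that no formal secondary claim, including one on mortality, can be made if the primary fails.

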10. CHANGES FROM PROTOCOL-SPECIFIED ANALYSES

Modifications to the planned statistical analyses should be minimized. None the less, the data

obtained from the study may indicate that the planned analyses are inappropriate, that additional analyses need to be performed, or that the design of the study needs to be modified, due to factors such as the distribution of the data or imbalance in important covariates. The study report will provide a detailed explanation for any deviations from the planned analyses.

11. LIST OF PLANNED TABLES, LISTINGS AND FIGURES

Each table, figure and listing are presented by treatment arm. Efficacy tables will be provided for the ITT population and safety tables will be provided for the safety analysis population. Accountability tables will also include an overall column. Listings will be sorted by treatment, subject ID, and by visit, if multiple visits exist.

11.1 Tables

11.1.1 Baseline and sample information tables

11.1.1.1	Accountability (Analysis population: All Enrolled)
11.1.1.2	Major Protocol Deviations (Analysis population: All Enrolled)
11.1.1.3	Demographics and Baseline Characteristics (Analysis population: ITT)

11.1.2 Efficacy (Analysis population: ITT)

11.1.2.1	Summary and Analysis of Adverse Events (AEs)
11.1.2.2	Summary and Analysis of Change in Blood-oxygen saturation
11.1.2.3	Summary and Analysis of Progression to ARDS
11.1.2.4	Summary of Intensive care unit (ICU)
11.1.2.5	Summary and Analysis of ICU LOS
11.1.2.6	Summary of Hospital LOS
11.1.2.7	Summary of Progression to intubation
11.1.2.8	Summary and Analysis of All-cause mortality and Time to Event
11.1.2.9	Summary of Time to sustained recovery to include pre-hospital status (LOS)
11.1.2.10	Summary of Ordinal scale for clinical improvement

11.1.3 Safety (Analysis population: Safety)

11.1.3.1	Overall Summary of Treatment-Emergent Adverse (TEAE) Events
11.1.3.2	Incidence of TEAEs by System Organ Class and Preferred Term
11.1.3.3	Incidence of Treatment-Emergent Related AEs by System Organ Class and Preferred Term
11.1.3.4	Incidence of Treatment-Emergent Serious Adverse Events (SAEs) by System Organ Class and Preferred Term
11.1.3.5	Incidence of TEAEs by Preferred Term in Descending Order of Frequency
11.1.3.6	Incidence of Treatment-Emergent Related AEs by Preferred Term in Descending Order of Frequency

11.1.3.7.1	Summary of Hematology
11.1.3.7.2	Summary of BioChemistry
11.1.3.8.1	Summary of Vital Signs and Change from Baseline over Time (bpm)
11.1.3.8.2	Summary of ECG Results
11.1.3.8.3	Summary of Medical History
11.1.3.9.1	Concomitant Medication Use by ATC Level 1
11.1.3.9.2	Concomitant Medications Descending Order of Use
11.1.3.9.3	Medication Started on Study in Descending Order of Use
11.1.3.9.4	Concomitant ARDS therapies Started on Study in Descending Order of Use

